6.0 EVALUATIONS AND MEASURES

6.1 Screening

All interested adolescents and parents/guardians will complete a screening questionnaire either in person on a study tablet, or online on the interested person's personal computing device (desktop, tablet, smartphone). The survey software will automatically determine whether the individual meets the eligibility requirements without the PI's input.

6.2 Enrollment/Entry

RS will prepare the participant to complete demographic, social, and attitudinal measures by CASI. Adolescent participants will complete these measures in two parts. The beginning CASI will include demographic information, SES, parental monitoring, and concern about HIV and the final CASI will include overall WTP, medical mistrust, and closing questions. Parent participants

will complete demographics, SES, WTS, concern about HIV, medical mistrust, and closing questions during the final CASI. The measures are summarized in **Table 2**, below.

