Potential participants will be recruited from clinical settings and HIV testing centers, or self-screen online. Potential participants will take a short CASI screening survey to determine eligibility. All eligible participants will provide contact information to establish a study visit appointment. Those eligible and screening in-person will either participate on the same day as the screening, or, if unable to stay, they will be contacted to establish a study visit appointment. Eligible participants who screen online will also provide their contact information to establish a study visit appointment.

Study participants will attend an in-person session at their respective AMTU. During the session, they will complete a CASI that collects demographic, social, behavioral, and attitudinal measures.

All study participants will undergo a simulated consent process for each of two hypothetical studies modeled after ATN 113 and HPTN 077. Procedures are slightly different for parents than for adolescents, so each group is described separately below:

Adolescent Participants: First, the adolescent participant will complete a demographic CASI. *For each hypothetical trial*, RS will lead the participant through a simulated consent process consistent with their randomized consent condition. Then, the participant will complete a CASI assessing WTP and will work with RS to complete the UCSD Brief Assessment of Capacity to Consent (UBACC). After the second UBACC, the adolescent will complete overall WTP, medical mistrust, and end of study questions.

Parent Participants: *For each hypothetical trial*, RS will review the informed consent forms with the parent. The parent will complete a CASI with three vignettes that describe each of the three possible consent conditions. Parents will rate the acceptability of each vignette. Then, the participant will work with RS to complete the UCSD Brief Assessment of Capacity to Consent (UBACC). After the second UBACC, the participant will answer demographic questions, medical mistrust, and end of study questions.

A subset of 6-8 adolescents and 6-8 parents per study site will complete a debriefing interview assessing adolescent and parent perspectives on the various consent conditions in greater depth, and to better understand the role of study features, family, and adolescent characteristics in willingness to

participate/willingness to support the hypothetical research studies.

MONITORING:

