2.0 SPECIFIC AIMS

The purpose of this study is to examine how the consent process affects the acceptability of participation in biomedical HIV prevention trials, from the perspective of behaviorally high-risk minors and the parents of minor adolescents. Acceptability will be measured by adolescents' willingness to participate (WTP) in and parents' willingness to support (WTS) their adolescent's participation in two hypothetical biomedical HIV prevention trials that are modeled after PrEP studies that included minors.

Aim 1: Describe how consent conditions influence high-risk minor adolescents' WTP in a hypothetical biomedical HIV prevention trial.

Primary Hypothesis: Adolescents assigned to the self-consent model will have the highest WTP scores, followed by those assigned to the adult permission model, and finally those assigned to the required parent permission consent model.

Additional sub-aims:

- Determine whether concern about HIV, capacity to consent, family context and sociodemographic characteristics moderate the relationship between consent condition and WTP scores.
- Describe high-risk minors' perceptions of the risks and benefits of parental consent, how they anticipate the different models of consent would influence their WTP in prevention trials, and whether shared-decision making between minors and parents is feasible.

Aim 2: Describe the acceptability of different consent conditions, from the parent perspective.

Primary Hypothesis: The parental permission required scenario will be the most acceptable to parents, followed by the adult permission model, and finally the adolescent self-consent model.

Additional sub-aims:

- Determine whether concern about HIV, capacity to consent, and sociodemographic characteristics moderate the relationship between consent condition and acceptability.
- Describe parents' attitudes toward the various consent models, their perceptions of the risks and benefits of each model, and their conceptualization of a shared decision making process for consent.

Aim 3: Describe the effects of the study agent (stage of development and method of delivery) on high-risk minor adolescents' WTP scores and parents' acceptability scores

Primary Hypothesis: WTP and acceptability scores will be higher for the study of an oral medication that is already FDA-approved for adults compared to study of a topical agent that is still under investigation.

Additional sub-aims:

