Eligible parent participants will first complete a demographic questionnaire. They will then review the informed consent form for the first study with the RS and complete a CASI assessing the acceptability of three approaches to consent, presented in three different vignettes (please see section 3.4.2 for further information). Parents will work with RS to complete the UCSD Brief Assessment of Capacity to Consent (UBACC)²⁵. The simulated consent process and follow-up assessments will then be completed for the second hypothetical study. After the second UBACC, the participant will answer a series of questions via CASI.

A subset of adolescent and parent participants will be selected to participate in a debriefing interview.

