5.3 Investigation Procedures

RS will prepare the participant's iPad for the beginning of the study visit. Adolescents will complete demographic, social, and attitudinal measures by CASI. Once completed, RS will begin

the simulated consent process for study 1 or study 2 (depending on randomization) by reviewing the hypothetical consent form (which reflects the randomly assigned consent condition; Appendix II). RS will allow time for questions about the hypothetical study from the participant, provide answers as needed. The RS will then ask the adolescent to complete the WTP questions on their iPad. Finally, the RS will administer the UCSD Brief Assessment of Capacity to Consent (UBACC)²⁵ for study 1 or study 2 (depending on randomization). The RS will then repeat the simulated consent process, WTP, and UBACC for the additional hypothetical study (study 1 or study 2 depending on randomization).

For parent participants, RS will prepare the participant's iPad for the beginning of the study visit. RS will begin the simulated consent process for study 1 or study 2 (depending on randomization) by reviewing the hypothetical consent form (which reflects the randomly assigned consent condition; Appendix II). RS will allow time for questions about the hypothetical study from the participant, provide answers as needed. The RS will then ask the parent to read the vignettes and answer WTS questions on their iPad. Finally, the RS will administer the UCSD Brief Assessment of Capacity to Consent (UBACC)²⁵ for study 1 or study 2 (depending on randomization). The RS will then repeat the simulated consent process, vignettes and answer WTS questions, and UBACC for the last hypothetical study (study 1 or study 2 depending on randomization). Parents will then complete demographic, social, and attitudinal measures by CASI.

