APPENDIX I

Schedule of Evaluations

Evaluation (Procedure)	Screening Day 0	Pre-Entry Day 1-3	Entry Day XX
Determine eligibility and collect contact information using the web-based screening tool	X		
Contact eligible adolescents/parents to schedule their visit		X	
Participant consents to participate in the study			X
The participant will complete the demographic, social, and attitudinal measures by audio computer-assisted self-interview (CASI).			X
Participant will undergo a simulated consent process for hypothetical Study 1, modeled after ATN 113, is an open-label study of oral TDF-FTC.			X
Participant will complete the WTP/WTS scale(s) via CASI			X
The RS will administer the UCSD Brief Assessment of Capacity to Consent (UBACC) for hypothetical Study 1.			X
Participant will undergo a simulated consent process for hypothetical Study 2, modeled after HPTN 077, a Phase IIa trial of oral + injectable cabotegravir.			X
Participant will complete the WTP/WTS scale(s) via CASI			X
The RS will administer the UCSD Brief Assessment of Capacity to Consent (UBACC) for hypothetical Study 2.			X
Willing participants will participate in a debriefing interview, which will begin immediately after their 2 nd UBACC.			X

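### Parents report concern about HIV, a named Aim 2 moderator, only after both simulated consents and all six acceptability ratings, so it is open to influence from them

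*Combined protocol and SAP*

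**What the plan says.** The second aim in section 2.0 includes a moderator question for parents: "Determine whether concern about HIV, capacity to consent, and sociodemographic characteristics moderate the relationship between consent condition and acceptability". Section 10.4.1 covers it with a secondary sensitivity analysis that adds concern about HIV and other variables to the mixed models. Table 2 shows that concern is measured by two 5-point items.

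On timing, section 6.2 treats the two groups differently. For adolescents: "The beginning CASI will include demographic information, SES, parental monitoring, and concern about HIV". Parents, by contrast, "will complete demographics, SES, WTS, concern about HIV, medical mistrust, and closing questions during the final CASI". Section 5.3 agrees for parents. It takes them through consent review, vignettes with WTS questions, and UBACC for each hypothetical study, and then states: "Parents will then complete demographic, social, and attitudinal measures by CASI".

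Other sections describe the parent visit differently:
- Study abstract, study procedures: "After the second UBACC, the participant will answer demographic questions, medical mistrust, and end of study questions". Concern is not named.
- Section 3.0: "Eligible parent participants will first complete a demographic questionnaire", and at the end, "After the second UBACC, the participant will answer a series of questions via CASI". Concern is not named here either.
- Appendix I, which section 5.0 presents as a timeline, lists the attitudinal measures ahead of the first simulated consent and makes no exception for parents. It also has the debriefing interview, "which will begin immediately after their" second UBACC. Section 4.3.2 puts it after the final CASI, and section 5.3 after all data are collected and saved.

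**The concern.** A moderator should be fixed before the response whose variation it is meant to explain. Here a parent hears two HIV-prevention consent forms, rates who should decide about enrolment under three arrangements for each, and answers capacity questions about each trial. Only then is the parent asked how worried they are about their teenager acquiring HIV. That answer may be shaped by what the parent has just heard, or adjusted to fit the ratings just given. A concern-by-condition association could then run from ratings to concern, and the collected data could not separate the two directions. No later analysis can undo the order.

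At stake is the interpretation of the Aim 2 moderator result for concern. The plan gives no reason for treating parents differently from adolescents, and does not acknowledge that the parent measure is taken post-exposure.

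**Working it through.** **Order of measurement.** Sections 5.3 and 6.2 agree that parents' concern comes last. Section 3.3 has each parent judge three consent conditions for each of two trials, so 3 × 2 = 6 ratings precede it, together with two simulated consents and two UBACCs. Section 3.0 moves only a demographic questionnaire to the front, so on concern itself it is compatible with 5.3 and 6.2. Only Appendix I places attitudinal measures first.

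**Size of the risk.** The plan gives no figure to reproduce, so this is an illustration.

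Inputs from the documents:
- N = 144 parents (section 3.2)
- two-sided alpha = 0.05 (section 10.4.1)

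Assumption: there is no true moderation, but answering the vignettes leaves reported concern correlated r with the parent's own difference D (required-permission rating minus self-consent rating). Testing whether concern moderates this contrast is then a test of the correlation between concern and D.

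Formula: the expected test statistic is z = atanh(r) × √(N − 3), with √141 = 11.87. The rejection probability is approximately P(Z > 1.96 − z).

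- r = 0.1: z = 0.1003 × 11.87 = 1.19; P(Z > 0.77) ≈ 0.22
- r = 0.2: z = 0.2027 × 11.87 = 2.41; P(Z > −0.45) ≈ 0.67

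A simulation of the same test (20,000 replicates, no true moderation) gave these false-positive rates:

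| Assumed carry-over into reported concern | N = 144 | N = 120 |
|---|---|---|
| Same shift for every parent | 0.050 | 0.052 |
| Correlates 0.3 with overall acceptability only | 0.052 | 0.049 |
| Correlates 0.1 with D | 0.222 | 0.194 |
| Correlates 0.2 with D | 0.678 | 0.591 |
| Correlates 0.3 with D | 0.959 | 0.917 |

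The N = 120 column is included because section 3.3 still restricts parent enrolment to about 15 + 15 per site (30 × 4 = 120), whereas section 5.2.2 has 18 + 18 (36 × 4 = 144).

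The calculation uses one pairwise contrast. A joint test over three conditions has two degrees of freedom and would give somewhat different figures.

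**What the range shows.** Timing alone does not inflate the error rate. Inflation needs carry-over that follows the parent's own preference between consent conditions.

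**The case against.** The strongest reply is that harm is not shown. Every parent sees all three conditions and both trials, and only the order is randomised, so concern cannot differ by assigned condition. Uniform priming creates no false interaction. The inflated rates follow from assumed correlations that appear nowhere in the documents. This stands. A reader might infer that the parent moderator is in fact contaminated, but the documents support only that it is open to contamination.

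A reader might also join Appendix I's debriefing row to section 6.2's final CASI and conclude that interviewed parents report concern after the interview. No document states that sequence. Appendix I itself lists the attitudinal measures before the consents, while sections 4.3.2 and 5.3 put the interview last. Appendix I is also weak evidence of order: it is one table for both groups, has a single entry-day column, and lists Study 1 before Study 2 although that order is randomised.

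Asking these items last also keeps them from priming the primary ratings. That is a fair argument against moving the long family and attitudinal scales forward; Table 2 gives parental monitoring alone 25 statements. It is much weaker for two items. The consent forms already carry HIV content, and the sponsor accepts the same order ahead of the adolescents' primary outcome.

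Finally, section 10.4.1 analyses the two groups separately, so the different timing between parents and adolescents damages no planned comparison. That also stands.

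**Conclusion.** The point holds as a measurement-order weakness in a secondary analysis. Under sections 5.3 and 6.2, the parent moderator is recorded after both exposure and outcome, and an association between it and the ratings would have no clear direction. The consequence ranges from none (0.05) to substantial (about 0.22 or 0.67 at assumed correlations of 0.1 or 0.2 with the parent's between-condition difference, N = 144). The documents do not say where in that range the study would fall.

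The primary parent analysis does not use concern and is unaffected. Separately from any bias, the descriptions of the parent visit do not agree with each other and need to be reconciled.

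**What to change.** Move only the two concern-about-HIV items to a short opening parent CASI before the first simulated consent, as adolescents already have. Leave the longer family and attitudinal scales, medical mistrust and closing questions at the end. If the present order is kept, state in section 10.4.1 that parent concern is a post-exposure measure and report concern-by-condition results as non-directional.

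In the same amendment:
- give one parent visit order across the abstract, sections 3.0, 5.3 and 6.2, and Appendix I;
- clarify what WTS in the parents' final CASI refers to, since section 5.3 has it answered after each hypothetical study. It may be an overall item parallel to the adolescents' overall WTP, so it should be clarified rather than simply deleted;
- align the debriefing row in Appendix I with sections 4.3.2 and 5.3.

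The cost is a reordering of existing Qualtrics blocks and a minor amendment, with no new items or visit time. The downside is that two early items may slightly prime the ratings. Equal priming across conditions is likely but not guaranteed.

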6.2.1 Quantitative Evaluations

Table 2: Quantitative Measures

Demographics	Scale	Description of Items included
Demographics		Age, race/ethnicity, sexual orientation, gender identity, education, employment, health insurance status, city, living situation
Socioeconomic Status	FAS-III ^{26 27} (Adolescents)	7- questions adapted from the Family Affluence Scale-III, measuring a family's financial status based off of number of vehicles, computers, bathrooms, adolescent having their own bedroom, if the family has a dishwasher, number of times traveled outside US, and overall perception of family's financial status.
Social Support	MSPSS- modified ²⁸	4 –Likert questions on a 7-point scale ranging from very strongly disagree to very strongly agree, measuring parental support and relationships with adolescents.
Parental Monitoring	Parental knowledge - modified ²⁹ (Adolescents & Parents)	5- point Likert scale measuring parental knowledge, disclosure, solicitation, and parental control. The scale has 25 statements for the (adolescent/parent) Strongly Disagree to Strongly Agree for each statement. Adolescent statements such as “My parent(s) know what I do during my free time. Parent statements such as “I know what my teen does during his/her free time.”
Medical Mistrust ³⁰	(Adolescents & Parents)	6, 5-point Likert items that measure the degree to which the participant trusts medical researchers.
Communication	Communication with Parents ³¹ (Adolescents & Parents)	5 Questions asking the number of times parents and adolescents have communicated about relationships, sex, sexually transmitted infections (HPV, HIV), same sex relationships, and using a condom. Answers range from Never, Once/twice, Many times, and Don't know
Concern about HIV	HIV Risk perception ³² Adolescents & Parents	2, 5-point Likert questions about adolescent worry of being infected with HIV/AIDS and parents worry of their adolescent being infected with HIV/AIDS.
Sexual Behavior	Sexual Behavior ³³ (Adolescents)	5 questions for adolescents regarding sexual intercourse partners.
Capacity to Consent	UBACC ²⁵	8 open-ended questions (answers scored 0-2) to measure participant's understanding of research design, risks & benefits, voluntariness
Acceptability	Willingness to Participate ³³ (Adolescents)	3 Likert-type items that begin with question stems such as “If offered a chance to participate in this study, how likely are you to participate...”

	Acceptability of consent approach Assessment of adolescent capacity to consent Confidence in adolescent disclosure (Parents)	Likert-type items (scored 1-5) that measure each of the three constructs.
--	--	---

6.2.2 Qualitative Evaluations

The debriefing interview is designed to explore adolescent and parent perspectives on the various consent conditions in greater depth, and to better understand the role of study features, family, and adolescent characteristics in willingness to participate/willingness to support the hypothetical research studies. At the start of the interview, the participants will be informed that the interview will be recorded and transcribed and the participant will be asked to select a pseudonym for the researchers to use. The adolescent debriefing interview will consist of five sections including (1) general opinions about participating in HIV prevention studies, (2) opinions on the two specific studies, (3) relationship to parents, (4) opinions about parental involvement in the consent process, and (5) options/opinions for consenting in future studies. The parent debriefing interview will consist of four sections including (1) general opinions about HIV prevention studies, (2) relationship to their teenager, (3) opinions about parental involvement in the consent process, and (4) options/opinions for consenting in future studies.

6.3 Premature Discontinuation from Intervention

The RS will complete the ATN 150 Off Study Form (located at the end of the Qualtrics RA survey) when the decision is made to permanently discontinue the subject from the study and no further data collection will occur. (See Section 8.4)

7.0 DATA COLLECTION AND SITE MONITORING

7.1 Development of Protocol and Case Report Forms

The ATN CC, in collaboration with the Protocol Team, is responsible for the development of this protocol and ATN regulatory forms (e.g. off Study form, untoward event form). Indiana University (IU) is responsible for constructing, testing, and implementing the CRFs and CASIs in Qualtrics. IU is also responsible for all qualitative data (from UBACC and debriefing interviews) for this study.

7.2 Data Records

Participant-related study information will be identified through the Study Identification Number (SID) on all participant CRFs, audiotapes, and CASI data. Participant names or other personally-identifying information will not be used on study documents with the exception of preferred name or nick name to be used during the interview, and contact information, such as email address, phone/text number, and/or Facebook profile, which is collected from eligible and interested participants. Contact information is used to schedule a time to complete the study visit.

Electronic CRFs and CASIs are completed and keyed directly into Qualtrics. Any printed study-related information will be kept in double-locked, limited access areas at the study sites.

7.3 Data Collection

7.3.1 Screening

Adolescents and parents of adolescents will be screened either online or in-person using CASIs developed in Qualtrics. Information regarding their eligibility for the study will be collected, along with the first 5 digits of their street address and first 4 characters of apartment/unit, where applicable, in order to rule out dyads. Eligible individuals will also be asked for basic contact information (see section 7.2).

